Immune-related response determination per irRECIST

Target Lesions	Non-Target Lesions	%Change Tumor Burden	Immune-Related Response Status
CR	CR	-100%	irCR
PR	Any	$\leq 30\%$	irPR
PR	Any	$\geq 30\% \text{ to } <+20\%$	irSD
PR	Any	$\geq +20\%$	irPD
SD	Any	$\geq -30\% \text{ to } <+20\%$	irSD
SD	Any	$\geq +20\%$	irPD
PD	Any	$\geq +20\%$	irPD

No new lesions allowed to achieve irCR status. Otherwise, presence or absence of new measurable or new non-measurable lesions does not affect response status in isolation. New measurable lesions added to cumulative tumor burden to calculate % change tumor burden for the determination of immune-related response status.

Immune-Related Complete Response (irCR): Complete disappearance of all target and non-target lesions and no new lesions. The short axis of all lymph nodes must be ≤ 10 mm.

Immune-Related Partial Response (irPR): The sum of diameters has decreased $\geq 30\%$ from the baseline, but does not meet the criteria for irCR.

Immune-Related Stable Disease (irSD): The patient does not meet criteria for irCR, irPR or irPD.

Immune-Related Progressive Disease (irPD): The sum of diameters for target lesions and new measurable lesions has increased by $\geq 20\%$ from the nadir sum of diameters

Missing assessments and inevaluable designation

When no imaging/measurement is done at all at a particular time point, the patient is not evaluable (NE) at that time point. If only a subset of lesion measurements is made at an assessment, usually the case is also considered NE at that time point, unless a convincing argument can be made that the contribution of the individual missing lesion(s) would not change the assigned time point response.

Best overall response: all time points

The *best overall response* is determined once all the data for the patient is known.

Complete or partial responses may be claimed only if the objective response is confirmed on a follow-up scan obtained no less than 4 weeks after the initial scan demonstrating an objective response. Absent this subsequent radiographic confirmation, irCR or irPR designations will be considered as unconfirmed responses.

Special notes on response assessment

When nodal disease is included in the sum of target lesions and the nodes decrease to 'normal' size (<10 mm), they may still have a measurement reported on scans. This measurement should be recorded even though the nodes are normal in order not to overstate progression should it be based on increase in size of the nodes. As noted earlier, this means that patients with irCR may not have a total sum of 'zero' on the case report form (CRF).

Patients with a global deterioration of health status requiring discontinuation of treatment without objective evidence of disease progression at that time should be reported as 'symptomatic deterioration'. Every effort should be made to document objective progression even after discontinuation of treatment. Symptomatic deterioration is *not* a descriptor of an objective response: it is a reason for stopping study therapy. The objective response status of such patients is to be determined by evaluation of target and non-target disease as shown in **Table 1**.

CONFIRMATION/DURATION OF RESPONSE

Confirmation

Objective responses should be confirmed by CT and/or MRI scans obtained no less than 4 weeks after the original scan.

Duration of overall response

The duration of overall response is measured from the time measurement criteria are first met for irCR/irPR (whichever is first recorded) until the first date that recurrent or progressive disease is objectively documented (taking as reference for progressive disease the smallest measurements recorded on study). The duration of overall complete response is measured from the time measurement criteria are first met for irCR until the first date that recurrent disease is objectively documented.

Duration of stable disease

Stable disease is measured from the start of the treatment until the criteria for progression are met, taking as reference the *smallest sum on study* (if the baseline sum is the smallest, this is the reference for calculation of irPD).

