4.4 Rules for Continuation of Study Therapy

Patients who tolerate treatment with pembrolizumab and MGA271, or who tolerate treatment with MGA271+MGA012, may continue to receive additional treatment with the study drugs as specified in the protocol (see [Section 4.1.1](#)), until any one of the following conditions are met:

- After documentation of a confirmed complete response (cCR), MGA271 and pembrolizumab, or MGA271+MGA012, are continued for one more Tumor Assessment Cycle
- Patient meets criteria for immune-related disease progression (irPD) ([Appendix 6](#))
- Occurrence of drug-related DLT as defined for the DLT Evaluation Period
- The Sponsor, Investigator, or Regulatory Agency terminates the study
- Withdrawal of patient due to an AE or SAE
- Withdrawal of patient consent
- Completion of protocol defined therapy

- Investigator discretion
- Pregnancy
- Death

Note: For individual patients who meet these criteria, but are otherwise considered to be experiencing clinical benefit by the investigator, consideration may be given to extension of therapy on a case-by-case basis in consultation with the Sponsor. If a patient completes 6 cycles of therapy and is experiencing clinical benefit as determined by the investigator, consideration may be given to extension of therapy for an unrestricted number of additional 9-week treatment cycles of MGA271 and pembrolizumab or MGA271+MGA012 on a case-by-case basis in consultation with the Sponsor. Assessments and procedures for Cycles 7 and beyond will be done according to those for Cycle 6 (see [Appendix 1](#)). Such unrestricted treatment may continue until the patient either 1) meets the criteria for permanent discontinuation (see [Section 5.3.1](#)), or 2) a rollover protocol becomes available.

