7.11 Efficacy and/or Pharmacokinetic and Pharmacodynamic Assessments

7.11.1 Efficacy Assessments

7.11.1.1 Treatment of Patients According to Principles of Immune-Related Response Criteria

Tumor assessments will be obtained at screening using CT and/or MRI scans at time intervals as specified in the [Appendix 1](#) (Time and Events Table). The study is divided into 6 Tumor Assessment Cycles; the first is a 6-week cycle called the Initial Tumor Assessment Cycle and Cycles 2 through 6 are 9-week cycles. The tumor assessment takes place at the end of each cycle. Treatment will continue until patients have completed study therapy and required follow-up, experienced disease progression, or have been withdrawn from the study (see [Section 4.4](#) and [Section 5.3](#)). At each on-treatment tumor assessment time point, the objective response status will be determined. In the context of the statistical analysis for this trial, objective response determination and the assessment of best overall response (BOR) will be defined using both conventional RECIST1.1 criteria ([Appendix 5](#)) as well as an adaptation of these criteria, designated as immune-related response criteria (irRC) (i.e., irRECIST as defined in [Appendix 6](#)). Patient management decisions, however, will be made solely based on the immune-related response criteria ([Appendix 6](#)).

For patients who demonstrate acceptable tolerability of treatment with MGA271, and an objective response assessment of irCR, irPR or irSD, or unconfirmed clinically-stable irPD, therapy may be continued (see [Section 4.4](#) and [Section 5.3](#)).

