All other lesions (or sites of disease) including pathological lymph nodes should be identified as *non-target lesions* and should also be recorded at baseline. Measurements are not required and these lesions should be followed as ‘present’, ‘absent’, or in rare cases ‘unequivocal progression’. In addition, it is possible to record multiple non-target lesions involving the same organ as a single item on the case record form (e.g., ‘multiple enlarged pelvic lymph nodes’ or ‘multiple liver metastases’).

RESPONSE CRITERIA

This section provides the definitions of the criteria used to determine objective tumor response for target lesions by immune-related response criteria (i.e., irRECIST).

Evaluation of target lesions

Immune-Related Complete Response (irCR): Disappearance of all target lesions. Any pathological lymph nodes (whether target or non-target) must have reduction in short axis to < 10 mm.

Immune-Related Partial Response (irPR): at least a 30% decrease in the sum of diameters of target lesions, taking as reference the baseline sum diameters.

Immune-related Progressive Disease (irPD): at least a 20% increase in the sum of diameters of target lesions, taking as reference the *smallest sum on study* (this includes the baseline sum if that is the smallest on study). In addition to the relative increase of 20%, the sum must also demonstrate an absolute increase of at least 5 mm.

Unlike conventional RECIST criteria, the appearance of new measurable lesions does not automatically denote disease progression under immune-related response criteria. Rather the dimensions of new measurable lesions are added to overall sum of tumor diameters for determination of objective response status. Patients will not be considered as having progression unless the new overall sum of diameters has increased by $\geq 20\%$ from the smallest sum of tumor diameters achieved while on study.

Immune-Related Stable Disease (irSD): Neither sufficient shrinkage to qualify for PR nor sufficient increase to qualify for PD, taking as reference the smallest sum diameters while on study.

Special notes on the assessment of target lesions

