Lymph nodes. Lymph nodes identified as target lesions should always have the actual short axis measurement recorded (measured in the same anatomical plane as the baseline examination), even if the nodes regress to below 10 mm on study. This means that when lymph nodes are included as target lesions, the ‘sum’ of lesions may not be zero even if complete response criteria are met, since a normal lymph node is defined as having a short axis of <10 mm. In order to qualify for irCR, each node must achieve a short axis <10 mm. For irPR, irSD and irPD, the actual short axis measurement of the nodes is to be included in the sum of target lesions.

Target lesions that become ‘too small to measure’. While on study, all lesions (nodal and non-nodal) recorded at baseline should have their actual measurements recorded at each subsequent evaluation, even when very small (e.g., 2 mm). However, sometimes lesions or lymph nodes which are recorded as target lesions at baseline become so faint on CT scan that the radiologist may not feel comfortable assigning an exact measure and may report them as being ‘too small to measure’. When this occurs it is important that a value be recorded on the case report form. If it is the opinion of the radiologist that the lesion has likely disappeared, the measurement should be recorded as 0 mm. If the lesion is believed to be present and is faintly seen but too small to measure, a default value of 5 mm should be assigned (*Note*: It is less likely that this rule will be used for lymph nodes since they usually have a definable size when normal and are frequently surrounded by fat such as in the retroperitoneum; however, if a lymph node is believed to be present and is faintly seen but too small to measure, a default value of 5 mm should be assigned in this circumstance as well). This default value is derived from the 5 mm CT slice thickness (but should not be changed with varying CT slice thickness). The measurement of these lesions is potentially non-reproducible, therefore providing this default value will prevent false responses or progressions based upon

measurement error. However, if the radiologist is able to provide an actual measure, that should be recorded, even if it is below 5 mm.

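### Appendix 6's only irCR table row requires a -100% change, but the appendix text grants irCR to patients whose target nodes keep a recorded size below 10 mm

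*Protocol*

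**What the plan says.** The table in Protocol Appendix 6 that assigns immune-related response has one row ending in irCR. It needs target lesions in CR, non-target lesions in CR and a -100% change in tumor burden. No other row starts from target CR; the rest start from PR, SD or PD.

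The text of Appendix 6 works at lesion level:

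- Evaluation of target lesions: target lesions must disappear, and "Any pathological lymph nodes (whether target or non-target) must have reduction in short axis to" below 10 mm.
- Lymph-node note: "In order to qualify for irCR, each node must achieve a short axis <10 mm". The actual short axis is recorded even when the node has regressed below that size, so the sum "of lesions may not be zero even if complete response criteria are met".
- Special notes on response assessment: when nodes return to normal size "they may still have a measurement reported on scans", and "this means that patients with irCR may not have a total sum of" zero on the case report form.
- irCR definition printed under the table: "The short axis of all lymph nodes must be" at most 10 mm. Elsewhere the appendix says below 10 mm.

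Two provisions give the category practical weight. Protocol Section 7.11.1.1 states: "Patient management decisions, however, will be made solely based on the immune-related response criteria". Protocol Section 4.4 lists among its continuation conditions: "After documentation of a confirmed complete response (cCR), MGA271 and pembrolizumab, or MGA271+MGA012, are continued for one more Tumor Assessment Cycle".

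The SAP (Sections 5.1 and 6.6.1) uses the irCR category without a lesion-level definition, and Section 7 leaves programming specifications to a separate document.

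**The concern.** A patient whose target nodes have normalised to a measurable size is a complete responder by the text and is not recognised by the table. The same scan is CR under Appendix 5, whose time-point table has no percent-change column. A programmer who codes the table and one who codes the prose would therefore produce different irCR counts from identical data.

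Three things depend on the choice: the reported split between irCR and irPR, the duration of complete response that Appendix 6 measures from first irCR, and the moment at which the confirmed-complete-response condition in Section 4.4 is met.

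Two smaller gaps sit beside this one. The node limit is stated in two ways, which matters for a node of exactly 10 mm. Target CR with residual non-target disease also has no row, whereas Appendix 5 Table A-1 has one (PR).

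**Working it through.** No sample size or error rate is involved. The check applies the plan's percent-change formula to scans that meet the nodal irCR text and compares the result with the table.

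Inputs:

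- A nodal target has a baseline short axis of at least 15 mm (Appendix 6, baseline documentation).
- At irCR, each node is below 10 mm (or at most 10 mm under the definition below the table) and non-nodal targets are 0 mm.
- Change = (y_t - y_0) / y_0 × 100 (SAP Section 6.6.2).
- The table's figure for irCR is -100%.

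Examples, all with non-target lesions gone and no new lesions:

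| Target lesions, baseline to follow-up (mm) | Change | irCR by text | irCR by table |
|---|---|---|---|
| node 20 to 8, lung 30 to 0 | (8 - 50)/50 = -84% | yes | no; no row fits |
| node 15 to 9 | (9 - 15)/15 = -40% | yes | no; no row fits |
| node 20 to 5 (default for a faintly seen node) | (5 - 20)/20 = -75% | yes | no; no row fits |
| node 15 to 10 | (10 - 15)/15 = -33.3% | only under the at-most-10 limit | no |
| node 20 to 0 (judged to have disappeared) | (0 - 20)/20 = -100% | yes | yes |

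Where the unmatched patients go depends on what is read next. The irPR prose under the table asks for a decrease of at least 30% from baseline without meeting irCR. With n target nodes, the follow-up sum is at most 10n and the baseline sum at least 15n, plus any non-nodal lesions. Follow-up divided by baseline is therefore at most 10n/15n = 2/3, a decrease of at least 33.3%. So a patient denied irCR by the table always meets the 30% threshold, and becomes irPR if the table's irCR is combined with the prose irPR. By the table alone that patient has no status, because every irPR row starts from target PR.

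Consequence for the immune-related ORR: none under the first route, since irCR and irPR both count. If only the table is coded and an unmatched patient stays in the denominator as a non-responder, each such patient lowers the rate by 1/n. With the cohort sizes in Protocol Table 1 as illustrations, that is 1/18 = 5.6 percentage points (SCCHN) or 1/14 = 7.1 points (NSCLC).

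**The case against.** The strongest reply is that the table is a summary and the prose settles it. The special notes expressly allow a non-zero sum at irCR, so a careful reader would treat -100% as shorthand for the ordinary non-nodal case. The planned estimates are also robust: ORR pools complete and partial responses, duration of response starts at the first of either, irPFS depends on progression, and no separate irCR rate or interval is specified. Target CR with residual non-target disease is already irPR under the prose. This is a descriptive Phase 1 study in which antitumor activity is a secondary objective.

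Most of that stands, and it limits the size of the point. It does not remove the conflict: the appendix does not say which of table and prose governs, and the SAP gives no rule of its own.

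A reader might go further and infer that no patient with a nodal target can ever be irCR, so that the count is zero for them by construction. The documents do not support that. The notes say the sum may be non-zero, not that it always is, and Appendix 6 has a target lesion or node recorded as 0 mm when the radiologist judges it has likely disappeared. Such a patient reaches -100%.

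Nor do the documents establish that the irCR rate will be understated, or that sites will apply the continuation condition differently. Both depend on which rule is followed. Protocol Section 2.3.1.1.2 also reports that the pembrolizumab cohorts are closed and their patients have completed combination treatment, so any remaining effect on management lies mainly in Cohort 4 (up to 15 evaluable patients).

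Some irPR and irSD cells appear without a minus sign. That may be damage from text extraction and nothing here relies on it.

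**Conclusion.** The inconsistency is real and narrow. A patient whose target nodes keep a recorded, non-zero short axis below 10 mm, with all other disease gone, is irCR by the text of Appendix 6 and fits no row of its table. A patient whose nodes are recorded as 0 mm is classified the same way by both.

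The choice of rule affects the irCR/irPR split, the duration of irCR and the confirmed-complete-response trigger in Section 4.4. The immune-related ORR is unchanged if the irPR prose is applied, and undefined for these patients if only the table is programmed. The per-patient shifts above rest on the assumption that an unmatched patient is counted as a non-responder.

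The documents do not give the number of patients with nodal targets who reach this state, so the total effect cannot be sized. The two node limits differ only for a node of exactly 10 mm.

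**What to change.** - In the irCR row of the Appendix 6 table, replace -100% with the lesion-level rule already in the text: all non-nodal target lesions absent and all nodes below 10 mm in short axis; the sum need not be zero.
- State one node limit throughout. Below 10 mm is the limit used in the rest of Appendix 6 and in Appendix 5; the definition under the table is the exception.
- Add a row for target CR with non-target disease not in CR, giving irPR. Keep the 30% decrease that the irPR prose requires, with any new measurable lesions counted in the burden.
- In the SAP or its programming specifications, derive irCR from lesion-level data, not from percent change.
- Reconcile the passages so that the confirmed-complete-response condition in Section 4.4 refers to a single definition. This point proposes no change to that condition.

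The cost is a few table and wording edits and one programming rule. No new data are needed, because the appendix already requires the lesion measurements to be recorded.

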DoR	Duration of response
ECG	Electrocardiogram
eCRF	Electronic case report form
irPFS	Immune-related progression-free survival
irRC	Immune-related response criteria
MedDRA	Medical Dictionary for Regulated Activities
MAD	Maximum administered dose
MTD	Maximum tolerated dose
NSCLC	Non-small cell lung carcinoma
ORR	Objective response rate
OS	Overall survival
PFS	Progression-free survival
PD	Progressive disease
PT	Preferred term
PR	Partial response
RECIST	Response evaluation criteria in solid tumors

SAE	Serious adverse event
SAP	Statistical analysis plan
SPP	Statistical programming plan
SCCHN	Squamous cell carcinoma of the head and neck
SOC	System organ class
TEAE	Treatment emergent adverse event
TLF	Tables, listings, and figures

In Editing

1 INTRODUCTION

This study evaluates novel combinations of immunotherapies in patients with advanced cancer and is designed to investigate whether combined administration of MGA271 and pembrolizumab, or combined administration of MGA271 and MGA012, through coordinately blocking two distinct B7-H3 and PD-1 pathways, can further potentiate the promising antitumor activity observed with pembrolizumab or MGA012 alone. The statistical analysis plan (SAP) v1.0 aligns with amendment 6 of the study protocol and describes in detail the statistical methods used for analysis of the efficacy endpoints, the safety endpoints, as well as the pharmacokinetic (PK) and pharmacodynamic (PD) parameters collected from the study.

2 STUDY OBJECTIVES

2.1 Primary Objectives

The primary objectives of this study are:

To characterize the safety, tolerability, dose limiting doxicity (DLT), and maximum tolerated dose (MTD), or maximum administered dose (MAD, if no MTD is defined) of MGA271 when administered IV weekly in combination with 2 mg/kg pembrolizumab administered IV every 3 weeks (Q3W) to patients with unresectable locally advanced or metastatic melanoma, squamous cell carcinoma of the head and neck (SCCHN), or non-small cell lung carcinoma (NSCLC), urothelial cancer, and other cancers.

To characterize the safety, tolerability, and DLT of 15 mg/kg MGA271 when administered IV Q3W in combination with a flat-dose of 375 mg of MGA012 administered IV Q3W to patients with unresectable locally advanced or metastatic melanoma, SCCHN, or NSCLC, urothelial cancer, and other cancers as stipulated in inclusion criteria.

2.2 Secondary Objectives

The secondary objectives of this study are:

- To characterize the PK and immunogenicity of MGA271 administered IV weekly in combination with IV pembrolizumab Q3W, and of MGA271 in combination with MGA012, both administered IV Q3W.
- To characterize the PD activity of MGA271 when administered IV weekly in combination with IV pembrolizumab Q3W, and of MGA271 in combination with MGA012, both administered IV Q3W.
- To investigate the preliminary antitumor activity of MGA271 when administered IV weekly in combination with IV pembrolizumab Q3W, and of MGA271 in combination with MGA012, both administered IV Q3W, using both conventional Response Evaluation Criteria in Solid Tumors (RECIST) 1.1 and immune-related response criteria (irRC).

2.3 Exploratory Objectives

The exploratory objectives of the study are:

- To explore the relationships between PK, PD, patient safety, and antitumor activity of MGA271 when administered in combination with pembrolizumab.
- To investigate the immune-regulatory activity of MGA271 in combination with pembrolizumab and of MGA271 in combination with MGA012 in vivo, including various measures of T-cell activation in peripheral blood and/or tumor biopsy specimens.

- To determine the relationships between membranous expression of B7-H3 and PD-L1 on tumor cells, immune cell infiltration within biopsy specimens (including but not limited to CD4+ and CD8+ T cells), B7-H3 and PD-L1 expression on the immune cell infiltrate, and clinical response via IHC staining of optional paired pre- and on-treatment tumor biopsy specimens.

In Editing

